## **8. STATISTICAL CONSIDERATIONS AND ANALYSIS PLAN**

This is a randomized, double-blinded, placebo-controlled clinical trial designed to assess the impact of hydroxychloroquine to reduce the risk of progression from Stage 1 T1D (multiple autoantibodies, normal glucose tolerance) to Stage 2 (abnormal glucose tolerance) or Stage 3 (clinical diagnosis of diabetes). Eligible participants will be randomized in a 2:1 allocation ratio to treatment with hydroxychloroquine vs. placebo. Randomization will be stratified by two factors to ensure balance in the proportions who are randomized to each of the treatment arms: (1) prior enrollment on a T1D prevention trial and (2) age (<8 vs. ≥8 yrs. old). Specifically, participants will be randomized to hydroxychloroquine vs. placebo with stratification on whether they: (1) had prior enrollment on a T1D prevention trial and received placebo vs. had prior enrollment on a T1D prevention trial and received active therapy vs. had no prior enrollment on a T1D prevention trial, and (2) are younger than 8 years old vs. 8 years old or older. Age is a known significant factor in relation to clinical outcomes of interest even in the T1D prevention setting. Further, this cutoff of 8 years old at study entry was selected based on analyses that showed a significant effect modification on clinical outcomes based on this.

Analyses of study data will be conducted to address the primary and secondary objectives of the trial, other stated objectives, and other interrelationships among elements of study data of interest to the investigators and of relevance to the objectives of the study. Analyses by age, gender, and race/ethnicity, as appropriate, are also planned.

All analyses will be conducted under an intention-to-treat principle, whereby all outcome data in all randomized participants will be included in all analyses, as appropriate. Details of the analysis can be found within the statistical analysis plan.

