## 8.2. Primary Analysis

The primary objective of the study is to assess the effect of hydroxychloroquine therapy versus placebo on the risk of progression to Stage 2 or 3 T1D, which is measured from an OGTT or clinically diagnosed with confirmation.

Time to progression to Stage 2 or 3 T1D will be calculated across participants within each treatment group. Time to T1D stage progression will be estimated based on Kaplan-Meier methodology, where participants who were "free of abnormal glucose tolerance and/or T1D" at their last follow-up will be censored at that time point.

This time-to-event outcome will be analyzed using a Cox proportional hazards regression model that stratifies by prior T1D prevention treatment (none vs. placebo vs. active therapy) and age at the time of randomization (<8 yr vs  $\geq$ 8 yr), where treatment effect in this model will be tested using the Wald statistic. Incorporating these as stratification factors in the Cox regression model will allow separate baseline hazard functions to be fitted for each stratum. We will further evaluate differences in event rates in those in the prior treatment stratification factor; specifically, we will assess if there are differential event rates in those enrolling after participation in another prevention trial and ensure that this is accommodated by corresponding stratification in the Cox regression model.

In addition to stratifying on these factors, we will also evaluate if they are effect modifiers on any differences observed in the time to T1D stage progression between these prior treatment groups; i.e., we will formally test for interactions of treatment effect with prior treatment for T1D prevention as well as age on time to T1D stage progression (i.e. progression from Stage 1 to Stages 2 or 3 T1D).

Proportional hazards can be tested to ensure that we can assume that these effects will be parallel. If the assumption of proportional hazard is not appropriate, the data will be examined to determine the cause of non-proportional hazard, such as the presence of a decaying, diverging, or crossing effect of hazard ratios over time. Based on the cause of the non-proportional hazard, post-hoc analyses such as frailty models, parametric models, or models with interactions and time-dependent covariates may be employed.

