Criteria for diabetes_onset (T1DM) are based on glucose testing, or the presence of unequivocal hyperglycemia with acute metabolic decompensation (diabetic ketoacidosis). One of the following criteria must be met on two occasions as soon as possible but no less than one day apart for diabetes to be defined: 1. Symptoms of diabetes plus casual plasma glucose concentration ≥ 200 mg/dL (11.1 mmol/L). Casual is defined as any time of day without regard to time since last meal. The classic symptoms of diabetes include polyuria, polydipsia, and unexplained weight loss. 2. Fasting plasma glucose ≥ 126 mg/dL (7 mmol/L). Fasting is defined as no caloric intake for at least 8 hours. 3. 2 hour plasma glucose ≥ 200 mg/dL (11.1 mmol/L). The test should be performed using a glucose load containing the equivalent of 1.75g/kg body weight to a maximum of 75g anhydrous glucose dissolved in water. It is preferred that at least one of the two testing occasions involve an OGTT. Cases identified will be confirmed as having diabetes if the glucose values to make these determinations were obtained in a TrialNet laboratory as part of an OGTT. Cases diagnosed with diabetes by symptoms and casual glucose ≥ 200 mg/dL or by other criteria than the above will be adjudicated by the TrialNet Endpoint Adjudication Committee.

The date of arriving at the study endpoint is the date of the second occasion that meets either of the above criteria or the date in which the participant presented in a state of DKA.

3. Primary Analysis

The study design is a randomized double-blind placebo-controlled trial. The primary objective of the study is to assess the effect of hydroxychloroquine versus placebo on the risk of developing abnormal glucose tolerance (AGT) as measured from an OGTT.

The cumulative incidence of AGT over time since randomization within each treatment group will be estimated from a Kaplan-Meier estimate of the "AGT-free" survival function. Time-to-AGT was discretized to 6-month times in keeping with the OGTT schedule. The difference between groups in the cumulative incidence functions, and the associated hazard functions, will be tested at the 0.05 level, two-sided, using the Cox regression including age as a covariate (1, 5). The critical value for the test statistic, and confidence intervals in this primary analysis will be determined by the group-sequential procedure.

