A total of 201 participants will be randomized in a 2:1 allocation to treatment with hydroxychloroquine (n=135) vs. placebo (n=66). Randomization will be conducted using block randomization with variable block sizes with stratification on (1) whether or not participants have been previously treated for T1D prevention, and (2) age group (< 8 years old vs. 8 years old or older).

The assumptions underlying the estimated sample size for this design are: (1) 40% two-year event rate in the placebo group, (2) detectable hazard ratio of 0.50 (i.e. 22.5% two-year event rate) in the hydroxychloroquine group, (3) less than a 10% two-year dropout rate in both groups, and (4) survival curves which are consistent with exponential survival distributions. Even testing for variable proportions of each stratum and with slight variation in the expected hazard rates for the placebo group across the strata, our proposed sample size of 201 participants will provide at least 83% power to detect a hazard ratio of 0.50 in the time to T1D stage progression between the two treatment groups using a stratified Cox regression model⁷⁵.

Under the above assumptions, the target total number of events is equal to 80; i.e., the final analysis will be conducted once 80 events (confirmed abnormal glucose tolerance, diabetes) have been observed. If the accrual rate is 50 patients per year, with the above assumptions it is estimated that the enrollment period will last approximately 4 years with a total study duration of approximately 6 years (4 years of accrual + minimum of 2 years of follow-up) to provide a sufficient number of events to detect the assumed difference.

The final test of significance up to the six-year time point will employ group sequential critical values to protect against inflation in the type I error probability due to interim assessments of the emerging data for review by the DSMB (see Section 8.5).

Note the accrual period and the study sample are only projections, since the actual accrual rate and the loss-to-follow-up rate are unknown. As the study progresses, more accurate projections of the study end date will be computed based on the observed rate of enrollment, the observed number of events, and the observed rate of loss-to-follow-up. These data will be provided to the DSMB and the TrialNet governing body, and if need be, this document will be amended.

6. Interim Monitoring Plan

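### SAP 3 makes the primary test a Cox model adjusted for age alone, while Protocol 8.2 and the SAP's own power statement call for a stratified Cox model

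*SAP*

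**What the plan says.** **SAP 3 (Primary Analysis).** The groups are compared "using the Cox regression including age as a covariate". Age is the only adjustment named. The text does not say whether age is linear or cut at 8 years, names no strata, omits prior prevention treatment and names no test statistic.

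**Protocol 8.2 (Primary Analysis).** The outcome is analysed with a "Cox proportional hazards regression model that stratifies by prior T1D prevention treatment (none vs. placebo vs. active therapy) and age" at randomisation, split at 8 years. The reason is given: "Incorporating these as stratification factors in the Cox regression model will allow separate baseline hazard functions to be fitted for each stratum". The protocol also undertakes to look for different event rates in people who come from another prevention trial and to "ensure that this is accommodated by corresponding stratification in the Cox regression model". The statistic is named: "where treatment effect in this model will be tested using the Wald statistic".

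**Randomisation.** Protocol 8 says "Randomization will be stratified by two factors to ensure balance in the proportions who are randomized to each of the treatment arms"; the factors are prior prevention-trial enrolment and treatment (three levels) and age. Protocol 3.6 gives the same factors. On age, Protocol 8 adds: "Age is a known significant factor in relation to clinical outcomes of interest even in the T1D prevention setting".

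**SAP 5 (Study Power and Sample Size).** The claim of at least 83% power at a hazard ratio of 0.50 is for a comparison "between the two treatment groups using a stratified Cox regression model".

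**Which document governs.** Protocol 8 refers the reader to the SAP for analysis details. Protocol 1.2 requires Steering Committee approval of significant protocol changes. Neither document says that SAP 3 is meant to replace the 8.2 model.

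**The concern.** The two documents specify different deciding tests for the primary endpoint, and the SAP does not agree with itself. Prior prevention treatment is a randomisation factor that the protocol expressly promises to handle by stratification, yet it is absent from SAP 3 and from the subgroup and covariate lists in SAP 4.1 and 4.2. Protocol 2.1.2 and Protocol 8 both describe age as prognostic, so its form in the model is not a neutral detail.

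Near the critical value the two tests can give opposite verdicts. If the choice is still open once treatment codes are known, the more favourable result can be taken. The trial sets its final boundary at 1.969 to protect type I error, so this is an avoidable leak.

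**Working it through.** **1. The plan's own figure.** Inputs from SAP 5 and SAP 6: 80 events, 2:1 allocation, hazard ratio 0.50, final critical value 1.969. The Schoenfeld formula gives

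Φ(√(80 × 2/9) × ln 2 − 1.969) = Φ(2.923 − 1.969) = Φ(0.954) = 0.830.

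The stated 83% is correct. The formula has no term for strata, so it cannot separate the two models; simulation is needed.

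**2. Simulation set-up.**
- From the documents: 201 participants randomised 2:1 within six strata; 40% two-year placebo risk; 10% two-year dropout; about 4 years of accrual; six-monthly OGTT with a ±2-week window; analysis at the 80th event; |Z| > 1.969.
- Assumed, because the documents do not give them: 35% aged under 8, 20% with prior active treatment, 10% with prior placebo; confirmation 1-45 days after the first abnormal test; block sizes 3 or 6; ages spread uniformly within bands.
- Stratum effects, also assumed: none, or moderate (hazard ratio 2 for age under 8, 0.6 for prior active treatment).
- Every trial was analysed with all three models on the continuous confirmed date, using Wald tests. There were 4,000 trials per cell. Monte Carlo error is about 0.6 points for power and 0.3 points for null rejection and discordance.

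**3. Power at hazard ratio 0.50.**

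| Model | No stratum effects | Moderate effects |
|---|---|---|
| Protocol 8.2, stratified | 84.2% | 84.0% |
| SAP 3, age <8/≥8 | 85.5% | 84.2% |
| SAP 3, linear age | 85.2% | 82.9% |

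SAP minus protocol runs from +1.3 (85.5 − 84.2) to −1.1 points (82.9 − 84.0).

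**4. Opposite verdicts between the protocol test and an SAP test.** These occur in both directions:
- 3.1-4.8% of trials at hazard ratio 0.50
- 5.6-8.0% at 0.65
- 2.1-2.3% under the null

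**5. Other mixes.** Three further mixes used moderate effects, with 20-50% aged under 8, 10-25% prior active and 5-15% prior placebo. The power difference was −0.4 to +1.1 points, and discordance at 0.50 was 3.3-5.3%.

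**6. Null rejection over all these mixes.** Protocol test 4.3-5.2%; SAP test 4.0-5.2%; better of the two 5.2-6.3%. Taking the better result adds 0.8-1.2 points to the protocol test in the same trials.

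**7. Upper bound.** With strongly prognostic strata (hazard ratios 3 and 0.3, for which the documents offer no basis), SAP power is 82.7% (binary age) or 79.6% (linear age) against 83.9% for the protocol test. Discordance at 0.50 is 5.7-8.2%.

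**8. Related wording.**
- SAP 3 says time to abnormal glucose tolerance was put on a 6-month grid. This follows the Kaplan-Meier sentence and may concern only the curve, but SAP 2 and Protocol 8.1 date the event at the confirmatory test. Neither document gives a tie method. These are ambiguities, not contradictions, and were not simulated.
- For Stage 3, Protocol 8.3 requires the primary-endpoint methods. SAP 4.4 names a log-rank statistic and a proportional hazards model, and mentions strata for neither.

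**The case against.** SAP 3 does not say that age is the only term, and SAP 5 names a stratified model, so SAP 3 could be read as incomplete. That reading helps little: a primary-analysis section that omits the strata still leaves the model undefined, and the protocol's age strata are not the same thing as an age covariate.

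The SAP elsewhere refers to a likelihood ratio test and a step-up covariate procedure (4.2, 4.4), and Section 10 refers to covariate selection under the primary analysis. This could suggest a third candidate model. But the step-up procedure sits under secondary analyses, the likelihood ratio test in 4.4 only gates the exploration of non-proportional hazards, and Section 10 concerns compliance. None of these settles the primary test.

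Protocol 8.4 and SAP 5 describe prior treatment as yes or no, while Protocol 3.6, 8 and 8.2 give three levels. The shorter wording reads as shorthand, but it should be aligned.

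The strongest objection is that the harm is small and conditional, and this stands. Power is essentially unchanged, each test holds its level, and the inflation arises only if someone chooses after unmasking, which nothing in the documents suggests is intended. The stratum inputs are assumed. The simulations also cover the final look only; the interim test at 40 events against 2.963 is not in those rates.

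**Conclusion.** The contradiction is real and should be fixed. SAP 3 departs, without explanation, from the stratified model that Protocol 8.2 requires and SAP 5 assumes, and it drops a randomisation factor. No stated number is wrong: 83% power reproduces, and the SAP test is not anti-conservative. The cost of leaving it is a primary verdict that depends on the model in about 3-5% of trials at the design effect and about 6-8% at hazard ratio 0.65. If the choice is made late, type I error rises by about one point. These sizes rest on assumed stratum mixes and none-to-moderate stratum effects and apply to the final look. The conflict itself rests on the text alone.

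**What to change.** Before unmasking, rewrite SAP 3 to match Protocol 8.2:

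- Cox regression on time from randomisation to the confirmed event date, stratified by prior prevention treatment (none, placebo, active) and age (<8, ≥8 years).
- Wald statistic against the group-sequential critical value, with one named tie method (Efron or exact).
- The 6-month grid restricted to the Kaplan-Meier display.
- Any age-covariate or 6-month-grid model kept only as a labelled sensitivity analysis, stating how age enters.
- A statement that a stratum whose risk set holds one arm contributes nothing, with events reported by stratum.
- The three-level description of prior treatment used in SAP 5.
- The same stratified method for Stage 3 in SAP 4.4, as Protocol 8.3 requires.

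This is SAP wording only; the sample size and event target do not change. If the strata carry no risk difference, stratifying costs about 1-2 points of power (84.2% against 85.5%; mean standard error 0.231 against 0.227).

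Some strata will be sparse. In the main assumed mix the smallest of the six averages 6.8 participants, and 1.6-1.7 strata have fewer than 5 events. With 20% aged under 8, 10% prior active and 5% prior placebo, the smallest averages 1.7 participants and 3.4 strata have fewer than 5 events. The loss stays small: across the mixes 2.1-3.1 of the 80 events are uninformative, and simulated power is 83.6-85.2%.

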### **3.5. Description of Study Cohorts**

While enrollment for the TrialNet Abatacept Prevention Trial (TN18) is open, enrollment in this study for individuals age 6 or older will be limited to those with mIAA confirmed within 6 months of enrollment as one of their two or more autoantibodies. However, those who are age 3-5 years or who reside in countries not participating in TN18 and have normal glucose tolerance and two or more autoantibodies (regardless of mIAA status) are eligible. Otherwise, after completion of enrollment for TN18, all individuals  $\geq 3$  years of age with normal glucose tolerance and two or more autoantibodies regardless of mIAA status are eligible to screen for this study.

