The association of demographic, genetic, immunologic, metabolic, lifestyle factors, the presence of illness and concomitant medications, among others, both at baseline and over time, with the risk of T1D stage progression will be assessed in Cox regression models over time. The effects of changes in longitudinal factors on risk of progression will be assessed using time-dependent covariates for these factors. Analyses will be conducted separately within the hydroxychloroquine and placebo groups, and differences between groups in covariate effects (group by covariate interactions) will be assessed. Models will then be assessed within the two groups combined, taking account of any group by covariate interactions. Subgroup analyses will be conducted comparing the effects of hydroxychloroquine versus placebo on the risk of progression to Stage 2 or 3 T1D with a test of the group by subgroup factor interaction in a Cox proportional hazard (PH) Model. Specifically, we will evaluate potential differential effects of treatment in relation to other factors at baseline, including: age (both continuous as well as

categorical: children < 8 years of age vs.  $\geq$  8 years, as well as < 8 years vs. 8 to 12 years vs. adolescents [13-17 years] vs. adults [ $\geq$  18 years]), gender, race/ethnicity, whether or not they have a first degree relative (FDR) with T1D, and specific autoantibody status. Similar analyses will be conducted using the values of quantitative baseline metabolic and anthropometric factors such as weight, BMI, and the immunologic and metabolic factors described in Section 6 that include the autoantibody titers, basal C-peptide, stimulated C-peptide (peak and AUC mean), and measures of insulin resistance modeled from the OGTT. These potential effect modifiers, or interaction effects, will be evaluated both using tests of interaction in the Cox regression model as well as stratified analyses. In addition, we will evaluate differences in time to T1D stage progression across all randomized participants using multivariable Cox regression models with tests of interaction and stratified analyses to assess potential differential effects, based on whether or not participants were previously treated for T1D prevention.

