Data from the TrialNet Pathway to Prevention Study may be used to determine participant eligibility. Outcomes from other studies may be used in meta-analyses, but not in the evaluation of this study's efficacy.

4. Secondary Outcomes and Analyses

4.1 Subgroup analyses.

Subgroup analyses will be conducted comparing the effects of hydroxychloroquine versus placebo on the risk of AGT with a test of the group by subgroup factor interaction in a Cox proportional hazard (PH) Model. Subgroups of the population by age (classified appropriately), gender, race/ethnicity (white, nonwhite and Hispanic yes/no), and specific antibody status at baseline. Differences in the treatment effect between subgroups will be tested using Likelihood Ratio Test (LRT) in a Cox PH model (1).

4.2 Covariate analyses.

Similar analyses will be conducted using the values of quantitative baseline factors. They include age, weight, BMI, HbA1c, HLA (DR3/4 vs. others), autoantibody titers, basal C-peptide, stimulated C-peptide (peak and AUC), glucose (fasting, 2-hour, AUC and measures of insulin secretory rate (0-30 min) and sensitivity (ISI) (6,7) modeled from the OGTT) at study entry. The dependence of the treatment effect on the quantitative levels of a covariate will also be assessed by a covariate by treatment group interaction in a PH model. The ISI can also inform on the treatment effect independent of C-peptide.

The association of demographic, genetic, immunologic, metabolic, and lifestyle factors, the presence of illness and concomitant meds, both at baseline and over time, with the risk of AGT onset will be assessed in Cox PH Models over time. The effects of changes in longitudinal factors on AGT risk will be assessed using time-dependent covariates for these factors.

Using a step-up procedure additional covariates will be tested and included in the model only if they improve the log-likelihood at 0.10 level (2-sided). This will be accomplished with the treatment assignment variable included but the inclusion/exclusion of the candidate covariates will be completely independent of the treatment variable's impact on the model. The LRT associated with treatment variable in the full, adjusted model will be used for the test of treatment effect described in the previous paragraph. Thus, the adjustment of the significance level, as with multiple testing, is unnecessary.

4.3 Longitudinal analyses.

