1. Evidence that the HR is not constant over the period of follow up will be assessed and the risk of diabetes will be assessed in a PH model. The primary test for treatment effect is based on the Cox model, which assumes a proportional hazard between treatment groups. If there is a true treatment effect but it is not proportional over the follow-up period the test will have substantially less statistical power than stated in the statistical section of the protocol. Therefore, to establish a reasonable guide to pursue the possibility of a non-proportional treatment effect we will use the guideline requiring a significance level of 0.10 or less of the LRT from the standard Cox model. Graphical diagnostics using Schoenfeld residuals will be employed to explore evidence for a monotonically decreasing effect of treatment over the follow-up period. Also, plotting the Kaplan-Meier time-to-AGT rates by treatment group on the log-log scale will provide visual assessment of any diminishing effect of treatment (equal distance separation of curves indicates proportional hazard). We will characterize any such decreasing effect of treatment by model parameterization with monotonically decreasing benefit over the follow-up time. Initially, a treatment interaction with log-transformed time-on-study will be fit to the data and the log likelihood improvement in the fit noted. Other time transforms will be explored only to characterize mathematically the rate of the diminishing effect. Of particular interest will be characterizing the point in follow-up where the hazard ratio is 1. Any variations in proportional hazards other than a monotonically decreasing effect will not be of interest because of the possibility that it is simply random error.

5. Study Power and Sample Size

This study has been designed to provide 83% power to detect a 50% risk reduction in the hazard rate for progression to Stage 2 or 3 T1D (abnormal glucose tolerance or diabetes diagnosis) using a two-sided test at the 0.05 level after a minimum of two years of follow-up on all participants and an expected total study duration (accrual and follow-up) of six years. We note that if accrual is more rapid than expected, minimum follow-up on participants may need to be extended in order to meet the number of events required for the final analysis.

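### The planned treatment-by-mIAA test can absorb a treatment-by-age difference, because the entry rule partly ties mIAA status to age; a second model with both interactions would separate them

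*SAP*

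**What the plan says.** **Subgroup tests.** SAP 4.1 compares treatment effects across subgroups by a treatment-by-factor interaction, tested by likelihood ratio in a Cox model. The factors are listed as "Subgroups of the population by age (classified appropriately), gender, race/ethnicity (white, nonwhite and Hispanic yes/no), and specific antibody status at baseline". Protocol 8.3 describes the same analysis "with a test of the group by subgroup factor interaction in a Cox proportional hazard (PH) Model". Neither text says that the antibody model also carries a treatment-by-age term. Age appears elsewhere as a covariate (SAP 3) or as a stratification factor (Protocol 8.2).

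**Entry rule.** Protocol 3.5 sets a restriction that lasts as long as TN18 recruits: "enrollment in this study for individuals age 6 or older will be limited to those with mIAA confirmed within 6 months of enrollment". Children aged 3 to 5 and residents of countries not in TN18 are exempt, and the rule lapses when TN18 enrolment is complete. Protocol 4.1 repeats this. Footnote 1 of Appendix 1 is narrower: it applies the rule to people aged 6 or older who are also eligible for TN18.

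**Age.** Protocol 8 explains the age stratum by saying that "this cutoff of 8 years old at study entry was selected based on analyses that showed a significant effect modification on clinical outcomes". Protocol 8.2 plans a formal test of whether the treatment effect differs by age.

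**The concern.** While the rule is in force, mIAA-negative participants can come only from the youngest children, from countries outside TN18 or, on the Appendix 1 wording, from older people not eligible for TN18. The mIAA-negative group is then younger than the mIAA-positive group because of the entry criteria, not by chance. Randomisation does not remove this, since the contrast is between antibody groups and not between arms.

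Stratifying by age, or adding age as a covariate, adjusts the baseline hazard. It does not absorb a treatment effect that differs by age. If there is such a difference, a model whose only interaction is treatment-by-mIAA assigns part of it to mIAA. At stake is the reading of one secondary result: a claim that response depends on mIAA status could reflect age, or a real dependence could be hidden by age.

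**Working it through.** **1. The plan's own figure.** SAP 5 says "This study has been designed to provide 83% power to detect a 50% risk reduction in the hazard rate" "using a two-sided test at the 0.05 level", with a "40% two-year event rate in the placebo group" and a "detectable hazard ratio of 0.50 (i.e. 22.5% two-year event rate) in the hydroxychloroquine group". With 80 events and 2:1 allocation, power = Φ(√(80 × 2/9) × ln 2 − 1.96) = Φ(2.923 − 1.960) = 83.2%, or 83.0% with the final critical value of 1.969. This agrees with the plan. The placebo hazard is −ln(0.60)/2 = 0.255 per year, and 1 − 0.60^0.5 = 22.5%. The documents give no figure for the antibody interaction test.

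**2. Direct arithmetic.** Suppose mIAA has no true effect. Let q be the share under 8 in an antibody group. Its apparent log HR is about q × ln HR(<8) + (1 − q) × ln HR(≥8), so the apparent ratio of hazard ratios, mIAA negative to positive, is

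exp[(q₋ − q₊) × ln(HR(<8)/HR(≥8))].

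Take assumed HRs of 0.35 and 0.65, for which ln(0.35/0.65) = −0.619, and q₊ = 20–30%:

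| q₋ | q₋ − q₊ | Apparent ratio |
|---|---|---|
| 100% | 0.70–0.80 | 0.65–0.61 |
| 75% | 0.45–0.55 | 0.76–0.71 |
| 50% | 0.20–0.30 | 0.88–0.83 |

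With HRs of 0.40 and 0.60, the same shares give 0.72 to 0.92.

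**3. Simulation of the test.** From the plan: 201 participants (135/66), the hazards above, 10% two-year dropout, and 2 to 6 years of follow-up. Assumed, because the documents do not say: 25% aged 3–5, 15% aged 6–7, mIAA prevalence 50% where unrestricted, 10% from non-TN18 countries, and a placebo hazard 1.5 times higher below 8. The Cox model was stratified at age 8, with 1,500 runs per scenario (Monte Carlo error about 0.6 points: √(0.05 × 0.95/1500)). There was no true mIAA interaction. The first two result columns use HR 0.3 (<8) and 0.7 (≥8):

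| Share enrolled under the rule | mIAA test alone rejects | With treatment-by-age (<8) added | mIAA test alone, HR 0.2 and 0.8 |
|---|---|---|---|
| 0% | 6.4% | 6.5% | 6.3% |
| 25% | 5.7% | 5.2% | not run |
| 50% | 6.6% | 5.8% | 7.1% |
| 75% | 7.9% | 5.7% | not run |
| 100% | 10.1% | 5.9% | 21.1% |

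Further results:

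- With HR 0.3 and 0.7, the median spurious log interaction is 0.13 at 50% (1.14-fold) and 0.47 at 100% (1.6-fold). The formula in step 2 agrees. At 50%, q₋ = 0.502 and q₊ = 0.350, giving 0.152 × 0.847 = 0.13. At 100%, q₋ = 0.815 and q₊ = 0.319, giving 0.496 × 0.847 = 0.42.
- With the age effect reversed (HR 0.8 under 8, 0.35 at 8 or older), the rate at 100% is 8.7%.
- At 100%, varying the other assumptions gives 7.9% to 29.6%. The top figure needs HR 0.2 and 0.8 and nobody from non-TN18 countries.
- With no age modification (HR 0.5 at all ages), the rate is 3.7–5.7%, so there is no inflation.
- If the effect changes at age 6, the age in the entry rule, adding an under-8 term corrects only part: 15.4% falls to 10.1%.

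**The case against.** The case against rests on four arguments.

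- **Age is not an established modifier.** A reader might infer from the sentence on the 8-year cut-off that age is known to change the response to hydroxychloroquine. The documents do not support this. The reference cited there is, by its title, about age and antibody type in progression from single to multiple autoantibodies. Protocol 8.2 only plans to evaluate age as a modifier. This stands, so the concern is conditional.
- **The link is partial.** It lapses when TN18 enrolment closes, it has exemptions, Appendix 1 narrows it further, and it cuts at 6 while the stratum cuts at 8. This also stands. The table row in which every mIAA-negative participant is under 8 is an extreme case.
- **The shift is small against the noise.** With 2:1 allocation the variance of a subgroup log HR is about 4.5/events. Splits of 40/40 and 15/65 events give interaction standard errors of √(4.5/40 + 4.5/40) = 0.47 and √(4.5/15 + 4.5/65) = 0.61. The extreme shift, ln 0.61 = −0.49, is 0.8 to 1.0 standard errors. Ratios of 0.83–0.88 are 0.2 to 0.4. This is correct, and it is why the rejection rate rises little in most scenarios.
- **The documents partly cover it.** Age has its own interaction test and would be reported beside mIAA. Neither document says that factors are tested separately, and Protocol 8.3 mentions combined models that take group-by-covariate interactions into account. That sentence concerns risk-factor association models, however, and the SAP does not carry it forward. Protocol 8.3 names multivariable interaction models only for prior prevention treatment. Two separate tests side by side do not show which factor carries the effect.

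**Conclusion.** The point holds as a cheap improvement to a secondary analysis. The entry rule partly links mIAA status to age, and the planned test, read plainly, cannot separate a treatment-by-mIAA difference from a treatment-by-age difference. Under the assumptions above, the effect is negligible when about half or less of enrolment falls under the rule. It becomes material, roughly 8% to 30% false positives against a nominal 5%, only if most participants entered under the rule and age modification is strong. The share under the rule, the age mix and the mIAA prevalence are not in the documents.

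Three broader inferences are not supported. The mechanism concerns mIAA and says nothing direct about the other autoantibodies. Nothing in the documents says that antibody subgroup results will set a later trial's entry criteria. The 80-event target, the 83% power and the primary test are untouched.

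**What to change.** In SAP 4.1, for mIAA status only, pre-specify before unmasking a second Cox model stratified by the randomisation factors. It should contain treatment-by-mIAA and treatment-by-age together with their main effects, and age should be continuous or include a cut at 6 years. Report it beside the planned interaction, and base any claim of an mIAA-specific effect on the adjusted estimate. Tabulate mIAA status by age and enrolment period so that readers can see how strong the link was. Repeat the mIAA comparison in participants enrolled without the restriction, but treat that repeat as descriptive, since events may be few.

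No new data are needed, and the design and primary analysis do not change. The cost is a wider interval for the adjusted interaction. As a rough guide the standard error grows by 1/√(1 − r²), where r is the mIAA–age correlation. For simulated values of r of −0.14 (half under the rule) and −0.37 (all), that is about 1% and 8%.
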